6.3.2.5. Analysis Population Summaries

[Table 7](#) summarizes the Safety, CC and PP analysis population eligibilities by randomized treatment group and reasons excluded. Subjects will be included in the count for a particular reason for exclusion if they met that criterion. As subjects may meet more than one criterion for exclusion, the “Excluded from...” counts may be less than the sum of the individual reason counts. A subject listing of analysis population eligibilities and the reasons for exclusion will be provided ([Listing 1](#)). A listing of subjects whose assigned treatment group does not match their randomized treatment group will be provided in [Listing 2](#).

6.4. Covariates and Subgroups

The protocol defines formal subgroup analyses as secondary and exploratory analyses, however the study is not powered to make definitive claims regarding any of the subgroup analyses. Subgroups defined by LGV infection at baseline, HIV status at baseline, adherence to study drug, antacid medication use, and symptomatic status will be analyzed separately. Analyses for each subgroup will include estimation of microbiologic cure rate, differences of rates, and their confidence intervals. See Section 8 for more details.

6.5. Missing Data

Subjects with unknown microbiologic cure status will be excluded from the CC and PP population. For ITT analyses, such subjects will be included with their cure status imputed as microbiological failures.

6.6. Interim Analyses and Data Monitoring

The DSMB will review a formal analysis of efficacy when approximately half (N=123) of subjects have contributed primary outcome measure data. At this time, an unblinded analysis of the primary outcome measure will be performed by the unblinded statistical team and provided only to the DSMB. This interim analysis is intended to inform the DSMB’s recommendation to the sponsor only whether the trial meets the criterion for stopping early (null hypothesis is or is not rejected). Details of the analyses are provided in Section 8.

6.7. Multicenter Studies

Safety and efficacy data will be pooled across all clinical sites. Center effects are not anticipated because treatment is self-administered, the sites are using standardized procedures for assessment of serious adverse events, and the study relies on a central laboratory for NAATs and PCR testing. See Section 8 and Section 9 for more details.

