6.5 Concomitant Medications/Treatments

Administration of any medications will be recorded on the appropriate DCF. Concomitant medications will include all medications taken 21 days before initiating study treatment through

Visit 3 or early termination, whichever occurs first. Prescription and over-the-counter (OTC) medications (including antacids) will be included, as well as, herbs, vitamins, and other supplements. Previously recorded medications will be updated as appropriate.

Subjects who have received study drug and are subsequently diagnosed with a concomitant infection that requires systemic antibiotics will receive treatment according to the local clinic's standard clinical practice, which will avoid antibiotics active against CT if a suitable alternative is available. Subjects who receive antibiotics active against CT after study drug administration will remain in the trial and followed for safety and efficacy. The medications that are prohibited for study eligibility in Section 5.2 are also prohibited throughout study participation.

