8.2.3 Specimen Preparation, Handling, Storage, and Shipping

8.2.3.1 Instructions for Specimen Preparation, Handling, and Storage

The UW will assemble and provide sites with standardized Aptima collection kits to be given to subjects who choose to the mail-in option for follow-up visits. Refer to the MOP for further information about packaging, transport, and storage of Aptima collection kits.

Specimen preparation, handling, and storage will be done according to local clinic SOPs. Additional details can be found in the protocol-specific MOP.

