4.4.3. Method of Assigning Subjects to Treatment Groups (Randomization)

Subjects will be randomized 1:1 to receive doxycycline or azithromycin. The trial will use a site-stratified, permuted, blocked randomization scheme.

The list of randomized treatment assignments is included in the enrollment module of Emmes' internet Data Entry System (IDES). Advantage eClinical® will assign each subject to a blinded treatment number from the list after demographic and eligibility data have been entered. Each site has a supply of blinded study drug kits pre-labeled with treatment numbers, each containing sufficient doses to treat a subject for 7 days. Once a subject is assigned a treatment number, the corresponding kit is distributed to the subject.

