6. GENERAL STATISTICAL CONSIDERATIONS

6.1. General Principles

Tabulations will be used extensively to summarize the data. All continuous variables will be summarized using the following descriptive statistics: n (sample size), mean, standard deviation, median, maximum and minimum. The frequency and percentages (based on the sample size) of observed levels will be reported for all categorical measures. Wilson confidence intervals for binomial proportions and difference in binomial proportions will be computed for efficacy variables. For the hypothesis tests comparing treatment groups with respect to efficacy outcomes, the two-sided Pearson Chi-Square test will be used. A 5% two-sided significance level will be used; i.e. two-sided 95% confidence intervals will be generated.

All summary tables will be structured with a column/sub-table for each treatment group (Azithromycin, Doxycycline, and All Subjects). In general, all data will be summarized by treatment group and/or site, and when appropriate by visit number. The total population size relevant to that table/column if applicable, including any missing observations will be displayed in the tables.

Data listings will be provided for all data. Note that in the data listings, Subject ID is the unique subject identifier, not the Study ID used on study and dates will not be included, only Study Day.

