6.3.2.4. Considerations for Analysis Populations

In the unlikely event of an error in randomization or study drug administration, subjects will be grouped by the formulation they actually received in Safety, CC, and PP analyses but will be grouped by their intended randomized assignment in ITT analyses.

Before unblinding, a blinded case review committee will review subjects with a reported concomitant infection/disease/procedure that may interfere with study drug, use of concomitant medications or products that may interfere with study drug, significant protocol deviations, treatment adherence, and other events that may impact study drug effectiveness or study analyses. On a case-by-case basis, the case review committee will determine if each subject will be included in the PP population, if and when a subject should be censored or removed from PP analyses, and/or any other analytical requirements for the subject. The committee will be blinded to both treatment group and outcome status for each case.

Subjects who receive treatment with an antibiotic active against CT for any reason before a particular post-baseline visit (Day 15 for analyses at Day 15, and Day 29 for analyses at Day 29) will be included in ITT and CC analyses as treatment failures and reviewed by the blinded case committee for inclusion in PP analyses.

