12. OTHER ANALYSES

There are no additional analyses planned for this study.

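### Randomisation is stratified by site, but the primary test and its confidence interval ignore site and no site-adjusted efficacy analysis is planned

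*SAP*

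**What the plan says.** On randomisation, SAP 4.4.3 states: "The trial will use a site-stratified, permuted, blocked randomization scheme". Protocol 5.3.1 says the same, and no other factor is named. There are two sites.

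On analysis, SAP 6.1 says that for treatment comparisons on efficacy "the two-sided Pearson Chi-Square test will be used". The code in SAP 6.1.1 is a two-way table of treatment by outcome with no site variable, and the interval for the difference is an unstratified Newcombe interval. Protocol 10.1 names the Pearson test as the one formal test.

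On site, SAP 6.7 says: "Safety and efficacy data will be pooled across all clinical sites. Center effects are not anticipated". It gives three reasons: treatment is self-administered, serious adverse events are assessed in a standardised way, and "the study relies on a central laboratory for NAATs and PCR testing. See Section 8 and Section 9 for more details". SAP Section 8 contains no site term, stratified test or by-site efficacy summary. Site is not among the subgroups in SAP 6.4, and SAP 12 closes the list: "There are no additional analyses planned for this study". By-site tables cover first-treatment dates and baseline characteristics only (Tables 5, 37 and 39). The efficacy tables (12 to 36) are by treatment group, and the shell for Listing 6, the individual efficacy data, has no site column.

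**The concern.** When allocation is balanced within site, the variance of the treatment difference depends on variation within sites. A pooled test also counts variation between sites as noise. If cure rates differ by site, its standard error is too large and the test is conservative.

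The reasons in SAP 6.7 only partly support the expectation of no center effect. The central laboratory does remove assay differences. Standardised assessment of serious adverse events has no bearing on a NAAT endpoint. None of the three reasons covers patient mix, or two local practices that can reach the endpoint:

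- Before swabs reach the central laboratory, Protocol 8.2.3.1 says: "Specimen preparation, handling, and storage will be done according to local clinic SOPs".
- Protocol 6.5 has infections diagnosed after study drug treated under the local clinic's "standard clinical practice, which will avoid antibiotics active against CT if a suitable alternative is available". Under SAP 6.3.2.4, subjects given an antibiotic active against CT before the visit "will be included in ITT and CC analyses as treatment failures".

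At stake are a little power, in a trial whose stated power at 95% vs 85% is 75%, and any planned check that the result holds at both sites. A site-stratified analysis added after unblinding would be post hoc.

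**Working it through.** **1. Reproduce the plan's figures.** Inputs from SAP 5, 8.1 and 8.2.1: 246 analysed (123 per arm), interim at 123 (61.5 per arm), bounds 2.79651 and 1.97743.

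For two equally spaced looks at overall two-sided 5%, the O'Brien-Fleming constant solves to 1.97743, and 1.97743 × √2 = 2.79651. Both bounds reproduce.

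Power uses the unpooled variance. At 95% vs 85% the final mean of Z is 0.10 / √[(0.95×0.05 + 0.85×0.15)/123] = 0.10 / 0.03772 = 2.651, and the interim mean is 2.651/√2 = 1.875. The two-look power is 75.2%. Across the power table the results are 75.2, 79.2, 83.4, 87.8 and 92.0%, against the stated 75, 79, 83, 87 and 92%. Interim stopping is 23.7% at 97% vs 87% (stated 23%) and 0.5% under the null (stated below 1%).

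**2. Why the pooled test is conservative.** With site shares w and site cure rates p, the ratio of within-site to pooled variance is Σ w·p(1−p) / [p̄(1−p̄)]. For a 50:50 split with cure of 95% and 87% at the two sites in both arms:

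- Within-site variance: (0.0475 + 0.1131)/2 = 0.0803.
- Pooled variance: 0.91 × 0.09 = 0.0819.
- Ratio: 0.98.

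The error rate at the final bound then falls from 4.80% to 2[1 − Φ(1.97743/√0.9805)] = 4.58%.

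**3. Compare the two tests at both looks.**

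- Pooled Z = (p̂_D − p̂_A) / √[2p̄(1−p̄)/n]. Its square is the Pearson statistic.
- CMH Z = Σ(d_s − t_s/2) / √Σ[t_s(2k_s − t_s) / (4(2k_s − 1))] for k_s per arm at site s, where d_s is doxycycline cures and t_s is all cures.

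There were 400,000 simulated trials per scenario, with near-1:1 allocation within site. The Monte Carlo standard error of power is about √(0.75×0.25/400,000) = 0.07 points.

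Assumed, because the documents are silent: site splits of 50:50, 70:30 and 85:15, and azithromycin site gaps of 0 to 15 points around an 85% mean. Doxycycline was set by a constant 10-point difference or by a common odds ratio giving 95% overall. Constant-difference cases needing cure of 100% or more were left out. The overall difference is 10 points in every row. Type I error is at 87% cure in both arms.

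| Site gap (points) | Power, pooled (%) | Power, CMH (%) | Gain (points) | Type I, pooled (%) |
|---|---|---|---|---|
| 0 | 75.4-75.6 | 75.5-75.7 | 0.1 | 4.9-5.0 |
| 5 | 75.4-75.8 | 75.6-76.2 | 0.1-0.5 | 4.8-4.9 |
| 10 | 75.5-75.9 | 76.0-77.0 | 0.4-1.2 | 4.7-4.8 |
| 15 | 75.5-76.1 | 76.3-78.5 | 0.8-2.5 | 4.4-4.6 |

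CMH type I error is 4.8-5.0% throughout, so the existing bounds carry over.

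**4. Second set of scenarios, overall rates not held fixed.** Only the contrast between the two tests is informative here.

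- Cure of 98% vs 90% at one site and 94% vs 80% at the other: CMH gains 0.4 to 0.7 points.
- 99% vs 92% and 90% vs 75%: CMH gains 1.2 to 2.2 points.
- 98% vs 92% and 80% vs 65% (extreme): CMH gains 4.0 to 4.7 points.
- No site difference, 91% cure in both arms: pooled type I error is already 4.6-4.7%, so part of the shortfall below 5% is discreteness and not pooling.

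**5. Confidence interval.** Pooled Newcombe coverage at N = 246 is 95.6-96.1% (50:50 and 70:30 splits). With no site difference at 95% vs 85% it is 95.6%, so pooling accounts for at most about half a point.

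**The case against.** The strongest reply is that nothing promised is lost. With overall rates fixed, pooled power is 75.4% or more in every row, and the SAP claims 75% at these rates. That is right: the stratified test offers a small gain beyond the stated power.

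The larger gains also need unfavourable site rates. At a 10-point gap with a constant difference, doxycycline cure at the smaller site is 88% (70:30; azithromycin 88% and 78%) or 86.5% (85:15; 86.5% and 76.5%), below the 95-100% range cited in SAP 5. Under a common odds ratio the gain is 0.4 to 0.8 points. This stands, and it is why the effect is called slight.

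It can also be said that pooling was prespecified with reasons, that baseline characteristics are tabulated by site, that mail-in kits are standardised, that one antibiotic rule applies at both sites, and that the Manual of Procedures, not available here, may harmonise handling. These points make a large site gap less likely. They do not supply an efficacy analysis that uses the stratum or shows the result by site.

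Finally, a small site is uninformative on its own. At 85:15 it has about 123 × 0.15 = 18 subjects at the interim and, at an average 10% failure rate, 1.8 failures; the final figures are about 37 and 3.7. A by-site table would then be only a weak consistency check. CMH simply gives such a site little weight, and it did not lose power in any scenario.

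**Conclusion.** The concern holds as a recommended improvement. It does not show that the planned test is invalid. The planned test keeps type I error at or below 5%, and the planned interval has adequate coverage. Stratifying by site gains essentially nothing if the sites are alike, up to about half a point of power at a 5-point site gap, and roughly 0.4 to 1.2 points at 10. The 15-point and extreme scenarios are there only to bound the effect.

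These sizes rest on assumed site gaps and shares, and on arms staying balanced within site. The complete-case population drops subjects after randomisation for a negative baseline NAAT or a missing Day 29 result, which could disturb that balance; a stratified estimate adjusts for this and a pooled one does not. Apart from any assumption, the SAP 6.7 cross-reference leads to no efficacy analysis involving site.

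**What to change.** **Preferred, before any unblinded look.** In SAP 6.7, 8.1 and 8.2.1, make the site-stratified CMH test primary, without continuity correction. Compare its signed square root with 2.79651 at the interim and 1.97743 at the final analysis. Report a site-stratified risk difference with a stratified Newcombe or Mantel-Haenszel interval. The reason for the stratified interval is to match the test; it was not materially narrower in simulation. Keep the pooled Pearson result as a sensitivity analysis.

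*Cost.* No new data. SAP 6.1 and 6.1.1 also need rewording, with site added as the stratifying variable in the PROC FREQ calls. The Table 12 and 13 shells and the Table 13 footnote change. Protocol 10.1 and 10.4.4.1 name the Pearson test, so a protocol amendment is needed. SAP 8.1 says the DSMB approved the interim summaries, so it must see the revised Table 12.

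**Fallback.** If the sponsor will not amend the primary test, prespecify the stratified test and risk difference as a sensitivity analysis, add a by-site cure table, and correct the SAP 6.7 cross-reference. This is a SAP edit only.

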6.8. Multiple Comparisons/Multiplicity

O'Brien-Fleming boundaries will be utilized for the interim and final analyses to account for the formal interim analysis while maintaining an overall Type I error rate of 5%. Section 8 for details.

7. STUDY SUBJECTS

7.1. Disposition of Subjects

[Table 8](#) will present the number of subjects who failed screening and number of subjects that failed to meet each eligibility criterion. [Table 9](#) will present the disposition of subjects overall and by randomized treatment group. A listing of subject who completed the study, terminated early from study, or discontinued treatment and the reason for early termination or treatment discontinuation will be included in [Listing 3](#).

[Figure 2](#) is a flowchart showing the disposition of study subjects in the safety and efficacy analyses, adapted from the CONSORT statement [1]. It shows the number of subjects eligible, enrolled and randomized, and analyzed for the safety and efficacy analyses, overall and by treatment group.

7.2. Protocol Deviations

A summary of subject-specific protocol deviations will be presented by the deviation category, the type of deviation, and randomized treatment group for all enrolled subjects ([Table 10](#)). All subject-specific protocol deviations and non-subject-specific protocol deviations will be individually listed, as well ([Listing 4](#) and [Listing 5](#), respectively).

8. EFFICACY EVALUATION

8.1. Interim Analysis

The primary efficacy endpoint for the interim analysis is the proportion of subjects with microbiologic cure in each study arm at Day 29. See Section 3.3.1 for the definition of microbiologic cure.

A test of hypothesis comparing the proportion of subjects with microbiologic cure at Visit 3 (Day 29) in each treatment group will be conducted in the CC population. The null hypothesis for the comparison is that there is no difference in proportions between treatment arms, with a two-sided alternative that considers the possibility of a difference in either direction. The test will be conducted using a Pearson Chi-Square test at the 5% two-sided significance level. The resulting test statistic will be compared to the O'Brien Fleming bound calculated in the study's sample size calculations. At the interim point the bound is |2.79651|, thus if the test statistic is either greater than 2.79651 (Group A cure rate is higher than Group B cure rate) or less than -2.79651 (Group B cure rate is higher than Group A cure rate), then the resulting action should be to stop the trial. Otherwise, the resulting action should be to continue on to the full sample size.

The proposed summaries to be generated for the interim analysis were approved by the DSMB at the organizational meeting on 30MAY2018 and they are copied in this SAP. The summaries will be semi-blinded, where the treatment group labels will be "Group A" and "Group B". Table 11 will summarize eligibilities for and reasons for exclusion from the CC population for all randomized subjects. Table 12 will present the microbiological cure rates with confidence intervals by treatment group. Also included is the test statistic and the O'Brien Fleming critical value.

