6.1.1. Pseudo Code

The following SAS® pseudo code will be used to calculate the following:

Chi-Square test at 5% two-sided significance level and odds ratio (and 95% asymptotic CI):

```
proc freq;
  Table treatment*analysis_variable / chisq;
  ods output ChiSq=outputdsn1;
  ods output RelativeRisks=outputdsn2;
run;
```

Fisher's Exact test at 5% two-sided significance level:

```
proc freq;
  Table treatment*analysis_variable / exact;
  ods output FishersExact=outputdsn;
run;
```

95% Wilson CI for proportions/percentages:

```
proc freq;
  Table treatment*analysisvariable / binomial(wilson);
  ods output binomialcls=outputdsn;
run;
```

95% Wilson CI for difference in proportions (produces Newcombe CI):

```
proc freq;
  Table treatment*analysisvariable / riskdiff(cl=Wilson);
  Exact Riskdiff;
  ods output pdiffcls=outputdsn;
run;
```

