8.2. Final Analysis

8.2.1. Primary Efficacy Analysis

The primary efficacy endpoint for the final analysis is the proportion of subjects with microbiologic cure in each study arm at Day 29. See Section 3.3.1 for the definition of microbiologic cure.

A test of hypothesis comparing the proportion of subject with microbiologic cure at Visit 3 (Day 29), will be conducted in the CC population. The null hypothesis for the comparison is that there is no difference in proportions between treatment arms, with a two-sided alternative that considers the possibility of a difference in either direction. The test will be conducted using a Pearson Chi-Square test at the 5% two-sided significance level. The number of subjects, the proportion of subjects with microbiologic cure, and the 95% Wilson confidence interval for the proportion of subjects with microbiologic cure will be presented overall and by treatment group. In addition, the difference in proportions between the Azithromycin group and the Doxycycline group and 95% Wilson confidence intervals will be presented.

The test statistic will be compared to the O'Brien Fleming bound calculated in the study's sample size calculations to determine significance. At the final analysis the bound is |1.97743|, thus if the test statistic is either greater than 1.97743 (doxycycline cure rate is higher than azithromycin cure rate) or less than -1.97743 (azithromycin cure rate is higher than doxycycline cure rate), then the resulting interpretation is that the cure rates are significantly different between arms. Otherwise, the resulting interpretation is that the cure rates are not significantly different between arms.

The above analyses, apart from the O'Brien Fleming bound comparisons will be repeated in the ITT and PP analysis populations.

See [Table 13](#), [Table 14](#), and [Table 15](#). See Section 6.1 for pseudocode to fit the above analyses. Individual efficacy response data is presented in [Listing 6](#).

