Eligible for CC Analysis Population		x	x	x	x	x	x
Excluded from CC Analysis Population	Any Reason	x	x	x	x	x	x
	Reason 1	x	x	x	x	x	x
	Reason 2	x	x	x	x	x	x
	...	x	x	x	x	x	x

Notes: Denominator for percentages is the number of subjects enrolled (N) in the study randomized to the specified treatment group.

Subjects will be counted for a particular reason for exclusion if they met the criterion. As subjects may meet more than one criterion, the sum of the individual reasons may add up to more than the subjects excluded.

Table 12: Interim Analysis Microbiological Cure Rates – CC Population

Treatment Group	Number of Subjects	Number of Subjects with Microbiologic Cure	Interim Microbiologic Cure Proportion	Interim Confidence Interval	Test Statistic	Critical Value
Group A	x	x	0.xx	0.xx, 0.xx	x.x	+/- 2.79651
Group B	x	x	0.xx	0.xx, 0.xx		

Implementation Notes:

Depending on the observed test statistic value, the last two columns will be rounded accordingly. The appropriate critical value (positive vs. negative) will be displayed according to the sign of the test statistic.

Table 13: Microbiologic Cure at Visit 3 (Day 29) by Treatment Group - CC Population

Treatment Group	Number of Subjects with Microbiologic Cure n	Number of Subjects N	Proportion of Subjects with Microbiologic Cure	Proportion of Subjects with Microbiologic Cure 95% CI	Difference in Proportion of Subjects with Microbiologic Cure between Doxycycline and Azithromycin	Difference in Proportion of Subjects with Microbiologic Cure between Doxycycline and Azithromycin 95% CI	Test Statistic	Critical Value	P-Value ^a
Doxycycline	x	x	0.xx	0.xx, 0.xx	0.xx	0.xx, 0.xx	x.x	+/- 1.97743	0.xxx
Azithromycin	x	x	0.xx	0.xx, 0.xx					
All Subjects	x	x	0.xx	0.xx, 0.xx					

Note: The denominator for proportions is based on the number of subjects enrolled in the respective treatment group.

^a P-value from the two-sided Pearson Chi-Square test.

Implementation Notes:

Depending on the observed test statistic value, the last two columns will be rounded accordingly. The appropriate critical value (positive vs. negative) will be displayed according to the sign of the test statistic.

Tables with similar format:

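### Do SAP 8.1 and 8.2.1 compare a Pearson Chi-Square with O'Brien-Fleming bounds that belong to a signed Z?

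*SAP*

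**What the plan says.** SAP 8.1 sets the interim test in the complete case population: "The test will be conducted using a Pearson Chi-Square test at the 5% two-sided significance level". It then gives the stopping rule: "thus if the test statistic is either greater than 2.79651 (Group A cure rate is higher than Group B cure rate) or less than -2.79651", with the negative side assigned to Group B having the higher cure rate. For Table 12 it adds: "Also included is the test statistic and the O'Brien Fleming critical value".

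SAP 8.2.1 uses the same construction at the end of the trial: "At the final analysis the bound is |1.97743|, thus if the test statistic is either greater than 1.97743". The positive side means doxycycline is better and the negative side azithromycin. It makes this comparison the criterion for significance and refers to the code: "See Section 6.1 for pseudocode to fit the above analyses". The Chi-Square block in SAP 6.1.1 contains "ods output ChiSq=outputdsn1" and a relative-risk output, with no step that takes a root or attaches a sign.

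The notes under Tables 12 and 13 say: "The appropriate critical value (positive vs. negative) will be displayed according to the sign of the test statistic". Table 13 also prints a p-value, footnoted "P-value from the two-sided Pearson Chi-Square test". SAP 6.8 and Protocol 10.2 say the boundaries hold overall Type I error at 5%.

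**The concern.** The named statistic and its threshold are on different scales. A Pearson Chi-Square on one degree of freedom cannot be negative, so it can never cross a lower bound or show which arm is better. The printed bounds are Z values; their Chi-Square counterparts are 7.8205 and 3.9102. Neither the SAP nor the protocol states the conversion, and the pseudo code outputs only the Chi-Square.

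This is the stopping rule and the only formal hypothesis test in the trial. A programmer who set the Chi-Square output directly against 2.79651 would stop far too easily. Table 12 has no p-value that would show the wrong scale at a glance.

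There is a smaller mismatch in the same sections. Each look is described as a test at the 5% level, although the bounds correspond to nominal levels of 0.00517 and 0.04799.

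**Working it through.** **Inputs.** Overall two-sided alpha 5% (SAP 6.8); interim at 123 of 246 evaluable subjects (SAP 5); 1:1 allocation (SAP 4.4.3); bounds 2.79651 and 1.97743 (SAP 8.1, 8.2.1); stated interim stopping probability under 1% at 87%/87% and 23% at 97%/87% (SAP 5). Exact calculations assume 61 and 62 subjects per arm at the interim and 123 per arm at the end.

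**1. The statistic.** For a two-by-two table, Chi-Square = Z², where Z = (p1 − p2) / √[p(1 − p)(1/n1 + 1/n2)] and p is the pooled proportion. The signed square root is therefore the same Pearson test with its direction kept.

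**2. The bounds.** For a two-look O'Brien-Fleming design at information 0.5 and 1, corr(Z1, Z2) = √0.5, the interim bound is c√2 and the final bound is c. Solving P(|Z1| < c√2 and |Z2| < c) = 0.95 gives c = 1.97743 and c√2 = 2.79651. Both match the SAP. Overall alpha is 0.0500.

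**3. The plan's other figures on the Z scale.**
- Interim stop under the null: nominal 0.0052; exact at 87%/87%, 0.0046. The plan says under 1%.
- Interim stop at 97%/87%, unpooled: mean of Z1 = 0.10 / √[(0.97×0.03 + 0.87×0.13)/61.5] = 2.080. P(Z > 2.79651 − 2.080) = 23.7%. Pooled variance gives 22.6%. The plan says 23%.
- Power, unpooled: 75.2, 79.2, 83.4, 87.8 and 92.0%. The plan's Table 3 gives 75, 79, 83, 87 and 92%.

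**4. The slip.** Comparing the raw Chi-Square with the printed bounds amounts to cut-offs on absolute Z of √2.79651 = 1.6723 and √1.97743 = 1.4062 (nominal p 0.0945 and 0.1597).

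| | Plan states | Signed Z | Raw Chi-Square |
|---|---|---|---|
| Interim stop, 87%/87% (exact) | under 1% | 0.46% | 9.3% |
| Overall Type I error (asymptotic) | 5% | 5.0% | 20.4% |
| Overall Type I error (exact, 87%/87%) | 5% | 4.9% | 20.6% |
| Interim stop, 97%/87% | 23% | 22.6–23.7% (normal approximation) | about 69% (simulation) |

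If the slip occurred at the interim only, overall error would be 11.9% (exact 11.7%). The raw Chi-Square column agrees with none of the plan's figures; the signed Z column agrees with all of them.

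**5. What Table 12 would show.** Take Group A 54/61 and Group B 60/62. Chi-Square = 123 × (54×2 − 7×60)² / (61×62×114×9) = 3.09, and the signed Z is −1.76. A raw 3.09 would exceed 2.79651 and signal that Group A is higher. The same table would print cure proportions of 0.89 for A and 0.97 for B.

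**6. The 5% wording.** Judging the final p-value against 0.05 instead of the bound gives 5.2% overall. With 123 per arm and at least 80 cures in each, only five count pairs per direction have Z between 1.960 and 1.97743. One is 116 v 107: Chi-Square 3.885, p = 0.0487, Z = 1.971, inside the bound. SAP 8.2.1 settles such a case, because it makes the bound the criterion.

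**The case for a change.** The best argument for a change is that a confirmatory decision rule should not depend on inference. The statistic is named, the code cited in 8.2.1 yields a different quantity from the one the bound needs, and defining the signed root would take one line. At the interim, if Group A really were higher, a raw Chi-Square would carry the right sign and the direction would give no warning. Table 12 has no p-value to show the scale error.

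Part of this stands: the signed root is nowhere stated. The rest carries less weight. The SAP 6.1.1 code is generic pseudo code, does not claim to perform the boundary comparison, and is not cited in 8.1. Table 12 prints each group's size, cures, proportion and interval, so the Z can be recomputed from the page even when direction gives no clue. To program the raw comparison, an analyst would have to pass over the negative bound, the sign-to-direction text and the table note.

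On the 5% wording, Protocol 10.1 and 10.4.4.1 use the same phrase, and Protocol 10.2 makes clear that 5% is the overall error. It is shorthand for overall alpha.

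**Conclusion.** No change follows. The plan leaves out a standard algebraic step, and the rest of its text supplies it: only a signed Z can be compared with a negative bound, indicate direction and select the critical value to display. Read that way, the bounds are exact, overall Type I error is 5.0% (4.9% exact at 87%/87%), and the stated stopping probabilities are reproduced. The 20.4% and 11.9% figures measure a programming error that the plan contradicts; they are not properties of the design. Judging the final p-value at 0.05 would add 0.2 percentage points (5.2% against 5.0%), and the SAP does not direct anyone to do so.

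This rests on an interim at about half the information, near-equal arms, and an analyst who takes the signed root, as the sign text and table notes require. Writing the step into the SAP would alter no bound, sample size or decision.
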